Gribel et al. (2011)[19] compared the accuracy of craniometric measurements made on lateral cephalograms and on cone beam computed tomography (CBCT) images. Ten fiducial markers were placed on known craniometric landmarks of 25 dry skulls with stable occlusions. CBCT scans and conventional lateral headfilms subsequently were taken of each skull. Direct craniometric measurements were compared with CBCT measurements and with cephalometric measurements using repeated measures analysis of variance (ANOVA). They concluded that CBCT craniometric measurements are accurate to a subvoxel size and potentially can be used as a quantitative orthodontic diagnostic tool. Two-dimensional cephalometric norms cannot be readily used for three-dimensional measurements because of differences in measurement accuracy between the two exams.

El-Beialy et al. (2011)[20] evaluated the accuracy and reliability of measurements obtained from 3-dimensional (3D) cone-beam computed tomography (CBCT) for different head orientations. They used Stainless steel wires fixed to a dry skull at different places. The skull was scanned by using CBCT in the centered and 5 other positions. Intraobserver and interobserver reliability tests were performed by using 6 landmarks identified on the virtual 3D skulls by 2 operators. They reported that CBCT measurement is a reliable technique that can be utilized for assessment of both linear and angular measurements.

Database search:

A search will be performed on electronic databases (PubMed, Cochrane library).

Aim of the study

A-PICO format:

Population:

Female orthodontic patients requiring 1st premolars extraction followed by anterior segment retraction.

Intervention:

Anterior segment retraction using segmental mechanics (frictionless) with miniscrews used as anchorage.

Comparator:

Anterior segment retraction using sliding mechanics (friction) with miniscrews used as anchorage.

Outcome measure:

	Outcome Name	Measuring Tool	Measuring Unit
Primary Outcome	Torque of anterior teeth	CBCT	Degrees
	Tip of anterior teeth	CBCT	Mm
	Vertical position	CBCT	Mm

	Root resorption	CBCT	Scoring system of Levander and Malmgren[21](5 grades classification)
--	-----------------	------	---

B-Research question:

In Orthodontics adolescent patients requiring 1st premolars extraction followed by anterior segment retraction, can frictionless mechanics offer a better control over the anterior segment compared to friction mechanics?

Objectives of the study

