Research hypothesis:

The null hypothesis (H_0) of this research is that there's no difference between both frictionless and friction mechanics on anterior teeth position during anterior segment retraction following 1st premolar extraction

Primary objective (s):

Measuring changes in extrusion/ intrusion, tip and torque of anterior teeth following anterior segment retraction using frictionless vs friction mechanics.

Secondary objective:

Measuring the root resorption during anterior segment retraction using frictionless vs friction mechanics.

Study design:

This is a randomized clinical trial with two arms parallel group, and 1:1 allocation ratio. In one group, frictionless mechanics will be applied during anterior segment retraction while the other will receive frictional mechanics during retraction to compare the changes in anterior teeth position.

Material and Methods

I)participants, interventions, and outcomes

A] Study Setting:

The study will be performed in the clinic of the Orthodontic Department at the Faculty of Oral and Dental Medicine, Future University. The recruited sample is from the Egyptian urban and rural population.

B] Eligibility criteria:

➤ **Inclusion criteria:** for the participants include the following:

1. Female patients, Age range (13-25)
2. Bimaxillary protrusion requiring extraction of four first premolars and maximum anchorage.
3. Patients with fully erupted permanent teeth (not necessarily including the 3rd molar).
4. Good general and oral health.
5. Class I molar relation (Angle's classification)

➤ **Exclusion Criteria:** for the involved subjects include:

1. Patients suffering from any systemic diseases or syndromes or on anti-inflammatory medication interfering with tooth movement.
2. Patients with extracted or missing permanent teeth. (except for third molars).
3. Patients with badly decayed teeth.
4. Patients with any parafunctional habits.
5. History of previous orthodontics treatment.

C] Interventions:

➤ Medical History Questionnaire:

For every patient to exclude the presence of any systemic condition interfering with orthodontic treatment.

➤ Clinical Examination:

Oral structures will be examined to identify caries, fracture or missing teeth. Gingival tissues will be carefully examined for any gingivitis, periodontitis, recession or lesions.

➤ Diagnosis

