Potential patients will be checked for fulfillment of the previously mentioned inclusion criteria. Every participant will be asked to sign an informed consent about the study. Full set of records (study models, lateral cephalometric radiographs, photos) will be taken for every patient as part of the routine procedure for treatment of patients in the clinic of the Orthodontic Department at The Future University of Egypt.

➤ Clinical Procedure:

After taking pre-treatment records:

- Bonding of all teeth except for first premolars and banding/bonding the first and second molars will be done using Roth prescription brackets (0.022 slot).

- Leveling and alignment for the bonded and banded teeth will be initiated following the wire sequence: 0.014 NiTi, 0.016×0.022 NiTi and 0.017×0.025 StSt.
- Then miniscrews will be placed in upper and lower arches between 2nd premolar and 1st molar.
- The patient will be referred for extraction of 1st premolars then canine retraction on a 0.017×0.025 StSt arch wire.
- After canine retraction, the patient will be referred for the pre-intervention records.

➤ **Acquisition of pre-intervention records:**

- The patient will be referred for CBCT which is considered to be the T0 record.

➤ **Start of Retraction:**

Frictionless group:

- A ligature wire will be extended between the canines and miniscrews for proper anchorage control.
- Closing retraction T-loops will be fabricated using 0.017 x 0.025 TMA wire. The loop will be positioned halfway the remaining extraction space after canine retraction. [17], [22].
- A gable angle of 45° will be added.
- Distal activation of 4 mm will be done which produced around 160 g of force per side with cinching back the wire distal to molars bilaterally.[23].
- Reactivation will be only done when the two arms of the t-loop approximate 2-3 mm.

Friction group:

- Miniscrews will be checked for stability. In case of any dislodgment or instability, they will be removed and replaced.
- A crimpable hook of 8mm length will be added to the archwire (0.017"x0.025" Stainless steel) distal to the lateral incisors passing through the center of resistance of the anterior segment.
- A ligature tie will be tightly wound from an undercut in the miniscrew head to canine bracket to stabilize the posterior segment.
- Retraction will start on a 0.017"x0.025" Stainless steel archwire using elastomeric power chain (force applied will be 160 g per side) extending between the crimpable hook and the miniscrew head.

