- The force will be measured by a force gauge and reactivated every 4 weeks maintaining constant force of retraction all over the retraction phase.

➤ **Follow up visits**

Patients will be asked to attend for follow up sessions every 4 weeks for:

- Evaluation mini-screws stability.
- Replacement of the power chain to maintain a force of 160 gm per side.
- Reactivation of the T-loop by further distal activation and cinch back if needed.

➤ **Criteria for discontinuing or modifying the allocated intervention:**

In cases of prolonged swelling or pain related to the mini-screw the patient will be given strict oral hygiene measures and the beginning of retraction will be postponed for three weeks.

In cases of loose or broken mini-screws, the screw will be removed and replaced.

➤ **Retraction records**

Following retraction of the anterior segment, patients will be referred to the same radiology center to acquire the final CBCT to assess the movement and inclination of anterior teeth.

➤ **Materials**

- American Orthodontics Brackets, Roth prescription, 0.022 slot size.
- American Orthodontics Elastomeric power chains.
- American Orthodontics Elastomeric O-ties.
- American Orthodontics Ligature wire.
- Mini-screw (1.6- by 8-mm, bracket head design; Dual Top Anchor System, Jeil Medical Corporation, Seoul, Korea).
- American Orthodontics Arch wires.
- American Orthodontics Molar bands/tubes.
- Crimpable hooks (Dentos Inc.)

D] Outcomes

[figure not shown]
Primary outcome: is to monitor the changes in the anterior teeth position (final anterior teeth tip, torque and vertical position) in association with each technique after retraction

Secondary outcomes: are to detect the presence of any root resorption associated with the different methods used for anterior segment. All outcomes

will be assessed as the difference between T0 at the start of anterior segment retraction after full canine retraction and T1 after complete space closure.

E] Participant timeline:

1. The principle investigator will screen the potential patients through careful clinical examination of patients at the orthodontic department, Faculty of Oral and Dental Medicine at The Future University of Egypt.
2. All recruited patients must fulfil the previously mentioned inclusion and exclusion criteria.
3. Every participant will be asked to sign an informed consent before the beginning of the study.

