Blinding of the outcome assessors: It is a single blinded study, the outcome assessors only will be blind. The patients name will be sealed from pre and post records. Then two assessors will carry on, blindly and independently, the measurements and analysis of the study.

III) Data collection, management and analysis:

A] Data collection methods:

Primary outcome:

1. *Anterior teeth torque, extrusion/intrusion:* will be assessed by the principle investigator via CBCT taken before and after the completion of retraction. The principal investigator identified the landmarks, reference lines and planes, then interpreted the measurements in degrees and millimeters.

2. *Anterior teeth tip:* will be assessed by the principle investigator via CBCT taken before and after the completion of retraction.

Secondary outcomes:

1. *Root resorption:* will be assessed by the principle investigator via CBCT taken before and after the completion of retraction. The resorption will be identified using scoring system of Levander and Malmgren[21] that classifies it into 5 grades: 0: no root resorption; 1: mild resorption, with the root of normal length and only an irregular contour; 2: moderate resorption, with small areas of root loss and the apex having an almost straight contour; 3: severe resorption, with loss of almost one third of root length; and 4: extreme resorption, with loss of more than one third of the root length.

B] Data management:

A colleague outside the research team will enter the data and organize it in excel sheets in the computer of the orthodontic department.

Data will include all photographs, models and radiographs.

C] Statistical Analysis:

- The principle investigator will be responsible for the extraction of the required data from the CBCT taken before and after retraction. The data will be sent to a specialized statistician.

- The specialized statistician will be responsible for the statistical analysis of the study by:

1. Presenting the data as mean, standard deviation (SD) and Standard error (SE) values.

2. Using Paired t-test to compare between the friction and the frictionless group of retraction as well as to compare between the pre-and post -treatment data for each group.

3. Using Anova test to determine the rate of anterior segment retraction.

4. Statistically evaluate the patient acceptance for both techniques.

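### Tip, torque and vertical position are all primary under one null at an unadjusted 0.05, no rule says which results reject it, and the stated power covers only one incisor distance.

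*Combined protocol and SAP*

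**What the plan says.** All references are to the combined protocol and SAP.

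- **Primary measures.** D] Outcomes: "Primary outcome: is to monitor the changes in the anterior teeth position (final anterior teeth tip, torque and vertical position". The primary objective is "Measuring changes in extrusion/ intrusion, tip and torque of anterior teeth following anterior segment retraction using frictionless vs friction mechanics". The PICO outcome table and A] Data collection methods ("Anterior teeth torque, extrusion/intrusion", then tip) agree. None of the three is ranked first. Root resorption has no label of its own in the PICO table, but the objectives and D] Outcomes make it secondary, so it is not counted here.
- **Hypothesis.** There is one null: "no difference between both frictionless and friction mechanics on anterior teeth position during anterior segment retraction following 1st premolar extraction". The research question is directional: "can frictionless mechanics offer a better control over the anterior segment compared to friction mechanics".
- **Testing.** Statistical Methods sets two-sided p below 0.05, and C] Statistical Analysis sets P ≤ 0.05. Neither gives an adjustment, a testing order, a composite, or an any-one versus all-three rule. C] Statistical Analysis lists "Presenting the data as mean, standard deviation (SD) and Standard error (SE) values" and does not mention confidence intervals.
- **Units.** Both arches are treated ("Then miniscrews will be placed in upper and lower arches between 2nd premolar and 1st molar"). No section says how several teeth, or two arches, become one value per patient.
- **Sizing.** E] Sample size calculation uses one variable, the change in central incisor edge to x-axis distance: means 0.68 and -0.32 mm, difference 1.0 mm, SD 0.76, power 0.8, Type I error 0.05. This gives 10 per group, raised to 15 for dropout. No difference or SD is given for tip or torque.

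**The concern.** A Type I error of 0.05 and a power of 0.8 are properties of a decision rule. The plan states both for one test of one distance, but its null covers three measures and has no rule. The actual error rate and power for that null therefore depend on a choice still open when the results are known. The investigators could decide afterwards which measure, tooth or arch answers the research question.

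The power gap has a second consequence. A non-significant tip or torque result could be read as showing that the two mechanics are equivalent, although nothing in the plan shows that the trial could detect a relevant difference in either.

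**Working it through.** **Inputs from the plan.** Means 0.68 and -0.32 mm, SDs 0.73 and 0.79, working SD 0.76, two-sided alpha 0.05, power 0.8, 10 and 15 per arm. **Assumed, not in the documents:** the correlations between measures, and an effect on tip and torque of the same standardized size as the vertical one. All figures use the independent-samples t test of Statistical Methods. C] Statistical Analysis instead says "Using Paired t-test to compare between the friction and the frictionless group of retraction", which does not fit two parallel groups.

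**1. The plan's own figure.**
- Difference: 0.68 - (-0.32) = 1.00 mm.
- SD: √((0.73² + 0.79²)/2) = 0.761.
- Normal approximation: n = 2 × (1.960 + 0.842)² × 0.76² / 1.0² = 9.07, rounded up to 10 per arm.
- Exact noncentral t, d = 1.0/0.76 = 1.316: power 0.795 at 10 and 0.935 at 15 per arm.

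The stated 10 per group reproduces for this one variable.

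**2. Any one significant measure rejects the null.** Independent measures, one test each: 1 - 0.95³ = 0.143. With correlated measures, by simulation of equicorrelated normal data:

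| Assumed correlation | 10 per arm | 15 per arm |
|---|---|---|
| 0.5 | 0.126 | 0.124 |
| 0.7 | 0.112 | 0.111 |
| 0.9 | 0.086 | 0.085 |

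If each arch were also tested separately (six tests), the independent figure is 1 - 0.95⁶ = 0.265. The simulated figures at 15 per arm are 0.21 (correlation 0.5) and 0.11 (0.9).

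**3. All three must be significant.** The chance of a false claim stays at or below 0.05. Joint power needs effects for tip and torque, which the plan does not give. With 1.316 SD assumed for each:

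| Assumed correlation | 10 per arm | 15 per arm |
|---|---|---|
| 0 | 0.795³ = 0.50 | 0.935³ = 0.82 |
| 0.5 | 0.60 | 0.85 |
| 0.7 | 0.65 | 0.87 |
| 0.9 | 0.71 | 0.90 |

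**4. Each measure is a separate claim.** 0.05 per test is correct and no adjustment is needed. The single null on anterior teeth position is then never tested.

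**5. Holm's procedure over three per-patient values.** The lower bound for vertical position is its power at 0.05/3 = 0.0167: 0.623 at 10, 0.776 at 13, 0.814 at 14 and 0.847 at 15 per arm. If all three effects were 1.316 SD, simulated power is 0.69 to 0.73 at 10 and 0.89 to 0.92 at 15. Overall error is 0.03 to 0.05 with one value per patient. If each measure instead took the better of two arch tests, it would be 0.081 at correlation 0.5, so the single value has to be defined first.

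**6. Precision for tip and torque.** The 95% CI half-width is t(0.975, 2n - 2) × √(2/n) in SD units: 2.101 × 0.447 = 0.94 SD at 10 per arm, and 2.048 × 0.365 = 0.75 SD at 15.

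**The case against.** The strongest reply is that the objective and the outcome are worded as measurement and monitoring. They fit three separate descriptive claims, for which 0.05 each is correct. That stands as one possible reading. It does not settle the matter, because the plan also states a formal null, sizes the trial to reject it, and asks which technique gives better control.

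A second reply is that the inflation figures rest on assumed correlations, and the six-test figure on a per-arch analysis that no section states. That also stands: they show the size under one reading. Under that reading, though, error exceeds 0.05 even at correlation 0.9.

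Four stronger inferences are tempting, and the documents do not support them:

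- **That the trial has a 14.3% Type I error.** No section says any one significant measure rejects the null.
- **That an all-three rule must bring power below 0.8.** With 15 completers per arm and the assumed effects it is 0.82 to 0.90. It falls to 0.50 to 0.71 at 10 completers. The supported statement is that joint power is not established.
- **That the sample size is miscalculated.** It reproduces for the variable it was built on.
- **That Holm is the necessary remedy at little cost.** At 10 completers per arm, the number the calculation rests on, power for vertical position could fall from 0.795 to 0.623. A single primary avoids that loss.

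A figure is missing under D] Outcomes, so a measurement diagram cannot be ruled out. The statistical sections themselves are present and give no decision rule.

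**Conclusion.** The point holds as a gap in the decision rule and should be fixed before analysis. Following the plan as written does not deliver its stated 0.05 and 0.8 for its stated null. The size depends on the rule eventually adopted:

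- any-one: error of 14.3% if independent, about 12.5%, 11% and 8.5% at correlations 0.5, 0.7 and 0.9, and higher if teeth or arches are tested separately;
- all-three: error controlled, joint power unknown;
- separate claims: error correct per test, overall null untested.

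The three primaries, the single null, the unadjusted threshold and the one-variable sizing are in the text. The correlations and the 1.316 SD effect for tip and torque are assumptions. Treating the incisor edge to x-axis distance as vertical position is a reasonable reading, which the plan does not spell out. A non-significant tip or torque result cannot be taken as evidence of no difference under any of the three rules.

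**What to change.** Adopt one of two options before analysis. Neither needs extra patients.

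**(a) Single primary.** Name the T0-to-T1 change in central incisor edge vertical position, the variable that was sized, as the only primary at two-sided 0.05. State which incisors and which arch give the one value per patient. Make tip and torque secondary, with estimates and 95% confidence intervals. Narrow the null and the research question to match. Power is 0.795 at 10 and 0.935 at 15 completers per arm. *Cost:* tip and torque lose primary status.

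**(b) Three primaries with Holm.** Define one value per patient per measure, with a stated rule for combining teeth and arches. Apply Holm at an overall two-sided 0.05 and claim a difference only for measures significant under it. Restate minimum power for vertical position as 0.62 at 10, 0.81 at 14 and 0.85 at 15 completers per arm. *Cost:* power at 10 per arm could drop from 0.795 to 0.623. With 15 enrolled per arm, the lower bound stays above 0.80 after one loss per arm and falls to 0.78 after two.

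The power figures in both options hold only if the value analysed has the 1.0 mm difference and 0.76 SD of the sample size section. A value combined over teeth or arches need not.

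Under either option, state that power for tip and torque is not established, and report each between-group difference with its 95% confidence interval. The choice depends on whether tip and torque need confirmatory claims; the power figures alone favour (a).

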4. After patient's enrolment, each participant will be asked for pre-intervention records to ensure proper diagnosis.
5. The co-supervisor will randomly allocate the patients to one of the intervention groups.
6. Active intervention will start after proper leveling and alignment of the upper and lower arches and canine retraction.
7. The principle investigator will take pre-retraction records for every participant (T0).
8. In Friction mechanics group, Power chain will be used for anterior segment retraction while in Frictionless group, T-loop will be used for retraction.
9. Each patient will come every 4 weeks for the follow up visit, for appliance activation and impressions for interim records.
10. After complete space closure, the principle investigator will take post-retraction records for each participant (Tfinal).
11. The principle investigator will continue the normal treatment and achieve proper finishing for every patient after the end of the study.

E] Sample size calculation:

In a previous study by **Dincer et al.** [1], they compared the effect of frictionless mechanics via PG spring (Poul Gjessing spring) (Group I) and friction mechanics using coil spring (Group II). The mean change in distance between central incisor edge and x-axis was of 0.68mm and SD of 0.73 in Group I, while Group II was -0.32mm and SD of 0.79.

Sample size calculation was done based on that study using PS software output. A continuous response variable from independent Group I and Group II subjects was planned. In the previous study, the response within each subject group was normally distributed with standard deviation 0.76. If the true difference in the Group II and Group I means is 1.0, we needed to study 10 Group II subjects and 10 Group I subjects to be able to reject the null hypothesis. The population means of the Group II and Group I are equal with probability (power) 0.8. The Type I error probability associated with this test of this null hypothesis is 0.05. Considering drop out a sample size of 15 per group was planned (**Figure 1**).

[figure not shown]

Figure 1: Power curve for 2-sample t-test denoting the power of the study.

Statistical Methods

All statistical calculations will be done using computer program IBM SPSS (Statistical Package for the Social Science; IBM Corp, Armonk, NY, USA) release 22 for Microsoft Windows.

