Numerical data will be tested for the normal assumption using Kolmogorov Smirnov and Shapiro Wilk tests. If normal distribution was found; therefore, data will be statistically described in terms of mean \pm standard deviation (\pm SD). Student t test will be used to compare between the study groups for independent samples in comparing normally distributed data. Paired t test will be used within group comparisons in comparing normally distributed data and Two-sided p values less than 0.05 will be considered statistically significant.

F] Recruitment strategy:

The principal investigator will recruit the patients from the clinic of Orthodontic department, Faculty of Oral and Dental Medicine- Future University.

Screening of patients will continue until the total number of participants for the study is collected.

II) Assignment of interventions:

A] Sequence generation:

The supervisor of the study will apply Computer generated random numbers to randomly assign patients to Group A (Friction) or B (Frictionless) using Microsoft Office Excel 2007 sheet. and will write the patient numbers in the first column, and will select function RAND()to generate the randomization number in the second column. These numbers will be sorted according to the randomization number so the first column numbers will be randomly distributed.

B] Allocation concealment mechanism:

The supervisor of the study will write the randomization numbers of the patients in opaque white papers folded three times to form sealed envelopes and store it inside a box. Then will keep the Codes for randomization at the secretary office.

C] Implementation:

At time of intervention, the main operator will send the patient to the secretary office. Then, the assigned employee will open the box and ask the patient to select one envelope. the main operator will assign each participant for the corresponding intervention either (friction or frictionless group) according to the list of codes of randomization.

Assignment to either intervention will occur before leveling and alignment stage.

D] Blinding:

Blinding of the operators: Blinding will not be possible for the operators during the application interventions and during the follow up visits. The principal operator is responsible for assigning subjects to interventions according to the concealed allocation, appliance activation at follow up visits.

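### Arms are compared on T1−T0 change by unadjusted t-tests. Prespecifying ANCOVA on the T0 value already collected would remove leftover chance imbalance and usually add precision.

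*Combined protocol and SAP*

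**What the plan says.** - **Outcome scale.** D] Outcomes states that all outcomes "will be assessed as the difference between T0 at the start of anterior segment retraction" and T1, after complete space closure. The sentence on the primary outcome, just before, describes it in parentheses as "final anterior teeth tip, torque and vertical position".
- **T0 data.** Under Acquisition of pre-intervention records: "The patient will be referred for CBCT which is considered to be the T0 record". E] Participant timeline, item 7, plans this record for every participant.
- **Between-arm test.** Statistical Methods: "Student t test will be used to compare between the study groups for independent samples". III) C] Statistical Analysis, item 2, names a different test for the same comparison: "Using Paired t-test to compare between the friction and the frictionless group of retraction".
- **Timing.** II) C] Implementation: "Assignment to either intervention will occur before leveling and alignment stage". T0 therefore follows assignment. The steps up to T0 (leveling, extraction, canine retraction) are described alike for both arms.
- **Randomisation.** II) A] Sequence generation describes a sort on RAND() and mentions no stratification.

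No section enters T0 as a covariate. The ANOVA in III) C] item 3 concerns the rate of retraction.

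**The concern.** A change score corrects for T0 as if each extra millimetre or degree at T0 carried through in full to T1. If the true slope is below 1, the change score over-corrects: the arm that happens to start higher tends to show the smaller rise. With 10 to 15 patients per arm and unstratified allocation, sizeable T0 differences are common. ANCOVA estimates the slope from data the trial already collects. What is at stake is precision, and how an observed T0 difference would affect the reading of the result. Validity is not at stake.

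Two wording problems add to this. A paired t-test cannot compare two independent parallel arms, so Statistical Analysis conflicts with Statistical Methods. The word for the end-of-retraction value in the primary outcome sentence also leaves a smaller doubt about whether T1 or change is compared. ANCOVA gives the same adjusted arm difference for either quantity.

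**Working it through.** **Inputs from E] Sample size calculation and Statistical Methods.** Difference in mean change 1.0 mm, SD of change 0.76 mm, two-sided α 0.05, power 0.80, 10 evaluable per arm, 15 per arm planned after allowing for dropout.

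**The plan's own figure.** n = 2(1.960 + 0.842)² × 0.76² / 1.0² = 9.07, rounded up to 10 per arm, so the stated figure reproduces. With the noncentral t distribution, power is 79.5% at 10 per arm and 93.5% at 15.

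**Assumptions not in the documents.** ρ is unknown, and so is the T0 SD, s. I take equal SDs at T0 and T1. Then:
- Var(change) = 2s²(1−ρ), so s = 0.76/√(2(1−ρ)).
- The ANCOVA residual SD is s√(1−ρ²) = 0.76√((1+ρ)/2).

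**Power.** The unadjusted test has SE 0.76√(2/n), which is 0.340 mm at n = 10 and 0.278 mm at n = 15, with 2n−2 df. ANCOVA has 2n−3 df and variance (residual SD)² × (2/n) × (1 + F/(2n−2)), averaged over F(1, 2n−2) to allow for estimating the slope. The expected value of that last factor is 1 + 1/(2n−4), an inflation of 6% at n = 10 and 4% at n = 15.

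| ρ | Implied T0 SD (mm) | ANCOVA power, n = 10 (unadjusted 79.5%) | ANCOVA power, n = 15 (unadjusted 93.5%) |
|---|---|---|---|
| 0.3 | 0.64 | 91.5% | 98.8% |
| 0.5 | 0.76 | 87.4% | 97.5% |
| 0.7 | 0.98 | 83.1% | 95.8% |
| 0.8 | 1.20 | 81.0% | 94.8% |
| 0.9 | 1.70 | 78.9% | 93.7% |
| 0.95 | 2.40 | 77.9% | 93.2% |

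Simulation agrees with these figures and gives type I error of about 5% for both methods.

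**Break-even.** Power is equal at ρ = 0.873 (n = 10) and 0.918 (n = 15). Estimator variance is equal at 0.882 and 0.926. The corresponding T0 SDs are about 1.5–1.6 mm and 1.9–2.0 mm.

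**Mean 95% CI width at 15 per arm.** Unadjusted 1.13 mm; ANCOVA 1.00, 1.06, 1.12 and 1.14 mm at ρ = 0.5, 0.7, 0.9 and 0.95.

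**Chance imbalance.** With equal arms, P(|T0 difference| > 0.5 SD) = 2[1 − Φ(0.5/√(2/n))], which is 26% at n = 10 and 17% at n = 15.

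**What subtraction leaves behind.** A T0 imbalance of one standard error shifts the change-score estimate by (1−ρ) × s × √(2/n):
- n = 10: 0.17, 0.13 and 0.08 mm at ρ = 0.5, 0.7 and 0.9. For ρ = 0.5 this is 0.5 × 0.76 × 0.447.
- n = 15: 0.14, 0.11 and 0.06 mm.

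In simulation at n = 10, the correlation between the estimated arm difference and the chance T0 difference was about −0.5 at ρ = 0.5 and −0.2 at ρ = 0.9 for change scores. For ANCOVA it was about 0.

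**The case against.** The strongest reply is that the plan is coherent as it stands. The objective, the outcome definition and the sample size all concern change, and the independent t-test on change is unbiased over randomisation. The benefit rests on a ρ that the documents do not give, and the plausible range runs from gain to slight loss. The large gain at ρ = 0.3 requires patients to differ less in T0 incisor position (SD 0.64 mm) than in movement (0.76 mm). At the planned 15 per arm, power is already 93.5%. All of this stands, and it limits the point to an efficiency recommendation.

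It is also true that the residual shift is not error on top of the standard error. The 0.17 mm at n = 10 and ρ = 0.5 is half of the 0.340 mm SE, and the interval already allows for it. ANCOVA's advantage is that it accounts for an imbalance once it is seen.

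T0 follows assignment and operators are unblinded, so a T0 difference need not be pure chance, and patients lost before T0 have no value. The change score depends on the same T0 measurement, so this does not favour it. It does call for reporting.

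The doubt over T1 or change is small, because the sentence that follows in D] Outcomes largely settles it as change. The paired-test conflict is an error in its own right, whatever is decided on ANCOVA.

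**Conclusion.** The point holds as an improvement the plan should adopt. It does not correct an invalid test. The payoff is asymmetric: at 10 per arm ANCOVA gains about 8 percentage points of power at ρ = 0.5 and 3.6 at 0.7, and loses 1.6 at 0.95 and 2.2 at 0.98. At 15 per arm it gains 4.0 points at ρ = 0.5, 2.3 at 0.7 and 0.2 at 0.9, and loses about 0.3 at 0.95. Under a linear model with a common slope, removing the effect of an observed T0 imbalance does not depend on ρ.

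These figures assume equal SDs at T0 and T1, normal data, equal arms and a change SD of 0.76 mm for vertical position. The documents give no figures for torque or tip, so the size of the gain there is unknown. Confidence is medium because ρ is unknown.

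**What to change.** 1. For torque, tip and vertical position, state the between-arm analysis as: ANCOVA of T1 (or T1−T0 change) on arm, with that outcome's T0 value as covariate and one value per patient, reporting the adjusted mean difference with its 95% CI. Keep the independent-samples t-test on change as a sensitivity analysis. Define how measurements on several anterior teeth become one value per patient.
2. In III) C] Statistical Analysis, item 2, remove the paired t-test between arms so that it agrees with Statistical Methods. Keep paired tests for within-arm T0–T1 comparisons only.
3. In D] Outcomes, state in one sentence which quantity is compared.
4. State that T0 is measured after assignment but before the allocated mechanics start. Report T0 by arm, and losses between assignment and T0.
5. Do not apply this model to the ordinal root-resorption grade.

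The cost is analysis wording, best settled before T1 data are seen. No extra scans, visits or patients are needed, and the t-test sample size can stand. The statistical price is one degree of freedom plus the slope-estimation variance (6% at 10 per arm, 4% at 15), which is a small net loss if ρ is very high.
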